3. OBJECTIVES AND PURPOSES OF THE TRIAL

For newborn infants born with a deficiency in lung surfactant because of prematurity or other causes of delayed lung maturation lung surfactant replacement therapy is life saving.^{2,3,4} The objective of this trial is to demonstrate that there is a group of patients who can benefit from surfactant replacement therapy with lower risk of administration complications and less discomfort by utilizing an alternative, safer administration technique – aerosolization.

Currently surfactant replacement therapy requires instillation of a liquid suspension into the airways. In order to instill into the airways it is necessary that an endotracheal tube be inserted and the surfactant administered through the endotracheal tube. A single dose may not be sufficient therapy and, if repeat dosing is likely or inevitable, a decision has to be made to either prolong the time of intubation or to remove the tube and possibly subject the patient to re-

intubation. One purpose of this trial is to determine if aerosolizing Infasurf provides an effective alternative for some patients that enable delivery of surfactant replacement therapy without subjecting them to the pain, discomfort and risk of endotracheal intubation or re-intubation.

The volume of the liquid instillation of the currently approved surfactants (2.5 to 4.0 mL/kg body weight) is larger than the total volume of the airways below the trachea which is 1 ml/kg body weight. Complications at administration are the physiologic consequences of two processes: (a) liquid obstruction of some airways, and (b) stimulation of irritant receptors in the lung. Liquid obstruction can produce transient low blood oxygen and high blood carbon dioxide, which together with neurally mediated irritant reflexes result in transient cardiopulmonary dysfunctions: cyanosis, tachycardia, bradycardia, hypotension, hypertension, airway obstruction and reflux of surfactant. Aerosolized delivery has the potential of minimizing both airway obstruction by liquid and the stimulation of irritant receptors in the lung.

Specifically the Objectives of the Trial are:

- (a) Document superiority of aerosolized of Infasurf to usual care in early RDS in preventing the need to intubate and instill a liquid surfactant suspension into the patient.
- (b) Show acute improvement in respiratory function by aerosolized Infasurf.
- (c) Document that aerosolized Infasurf is as safe as “usual care” for RDS patients.

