4. TRIAL DESIGN

4.1 Efficacy endpoints

The primary efficacy endpoint will be the incidence of the requirement for endotracheal intubation and instillation surfactant to “usual care” over 72 hours, the time course for acute RDS.

Secondary efficacy endpoints will measure other clinical parameters that are indicative of lung surfactant sufficiency:

- (a) Incidence of death and/or bronchopulmonary dysplasia (defined as an oxygen requirement to maintain acceptable blood oxygen saturations) at 28 days or discharge, whichever comes first.
- (a) Severity of acute RDS measured by quantitation of oxygen supplementation and respiratory support from randomization to 72 hours of age or intubation and surfactant instillation, whichever comes first.
- b) Duration of acute RDS measured by duration of supplemental oxygen.
- c) Protection from acute lung injury as measured by the incidence of lung air leaks or pulmonary hemorrhage from randomization to 72 hours of age or intubation and surfactant instillation.

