Randomization: Subjects will be randomized to the intervention or active control arm in a 1:1 fashion using a stratified permuted block randomization scheme with variable block sizes of 2 and 4. Randomization lists will be generated by the study biostatistician which will then be used to create an envelope-based system to be used at the individual study sites. Subjects will be included in primary data analyses according to their randomized assignment irrespective of the treatment actually received (intent-to-treat). Exceptions would include those who withdraw their consent to use any of their data prior to subject evaluation.

Accrual. Subjects will be accrued to the study on a first-come basis. The projected accrual is approximately 80 per month, and therefore recruitment is expected to be complete at most 365 days following the study starting point. Subjects will be followed to hospital discharge or 28 days whichever is shorter so total study duration will be approximately 13 months.

Descriptive analyses. Measured outcome variables will be summarized overall and by relevant demographic and baseline variables. Descriptive statistics such as frequencies and relative frequencies will be computed for all categorical variables. Numeric variables will be summarized using simple descriptive statistics such as the mean, standard deviation and range. A variety of graphical techniques will also be used to display data, ex. histograms, boxplots, scatterplots, etc.

Primary efficacy analyses. The primary efficacy analysis will be performed within each cohort separately and is based on a test for superiority of the experimental treatment relative to active control with regards to intubation rate. An overall assessment of the probability of intubation differences across study sites will be done using the Cochran-Mantel-Haenszel test. A one-sided nominal significance level of 5% will be utilized. Additional analyses will be performed utilizing both cohorts of subjects in order to assess differential treatment effects.

Primary safety analyses. All adverse events will be recorded during the study period and then tabulated at the end of the study.

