Secondary analyses. Secondary efficacy outcomes representing measures of severity of RDS (oxygen supplementation and respiratory support measures from randomization to Surfactant Instillation or 72 hours of age, whichever comes first) will be summarized using standard descriptive statistics and compared between treatment groups using the stratified Wilcoxon rank sum test. In the case of outcomes measuring the duration of acute RDS (duration of supplemental oxygen), so to accommodate the potential censoring involved, distributional estimates will be based on the Kaplan-Meier method and groups differences statistically assessed using the stratified log-rank test. For the comparison of measures of protection from acute lung injury (incidence of lung air leaks or pulmonary hemorrhage from randomization to 72 hours or intubation and surfactant instillation), the Cochran-Mantel-Haenszel test will be used. All statistical tests will be one-sided and tested at a 5% nominal significance level.

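### The analysis plan makes no comparative inference on harm, so it cannot support objective (c), that aerosolized Infasurf is as safe as usual care

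*Combined protocol and SAP*

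**What the plan says.** Section 3 lists three objectives. The third is "Document that aerosolized Infasurf is as safe as “usual care” for RDS patients".

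Section 9.1 sets out the analyses:

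- **Primary efficacy.** The analysis "is based on a test for superiority of the experimental treatment relative to active control with regards to intubation rate", and "A one-sided nominal significance level of 5% will be utilized".
- **Secondary efficacy.** Severity is compared with a stratified Wilcoxon test and duration with a stratified log-rank test. Lung injury ("incidence of lung air leaks or pulmonary hemorrhage from randomization to 72 hours or intubation and surfactant instillation") is compared with a Cochran-Mantel-Haenszel test. The rule for all of them is "All statistical tests will be one-sided and tested at a 5% nominal significance level". The direction is not written out for the secondary tests, but section 4.1 and section 9.1 both present the lung-injury outcome as a measure of protection.
- **Safety.** The whole entry is "All adverse events will be recorded during the study period and then tabulated at the end of the study". It does not say whether the table is split by arm, and it gives no difference, interval, margin or test.

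Section 4.1 also lists "Incidence of death and/or bronchopulmonary dysplasia" as a secondary endpoint. Section 9.1 names no analysis for it.

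Harm is watched elsewhere. Section 4.6 has stopping rules for the individual, the site and the whole trial. Section 8.3 covers reporting of severe unexpected events, and section 9.3 gives the monitoring committee a review of adverse events.

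**The concern.** To say that one treatment is as safe as another, a trial has to compare them and show how large an excess of harm the data rule out. This plan specifies neither step. The safety outcomes go into a table. The one tested outcome that could plausibly get worse, air leak or pulmonary hemorrhage, is tested in one direction. If that direction is benefit, an excess on aerosol yields a large p-value and the formal result is simply not significant.

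At stake is one of three stated objectives in a trial that section 1.7 describes as pivotal. Without intervals, the report would offer no measure of how much harm remains compatible with the data.

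**Working it through.** **Inputs from the documents.** Allocation is 1:1 (4.2). There are 229 per arm in the cohort not given surfactant at birth, and 200 in total, so 100 per arm, in the post-instilled cohort (9.2). Tests are one-sided at 5% (9.1). The planned intubation rates are 60% v 48% in the larger cohort (9.2).

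**Assumed inputs.** The documents give no safety event rate and no margin. Rates of 5% and 10% are used below as a range.

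**1. The plan's own figure.** Section 9.2 states 80.1% power for 60% v 48% with 229 per arm. One-sided 5%, pooled test with continuity correction:

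- SE under the null = √(2 × 0.54 × 0.46 / 229) = 0.0466
- SE under the alternative = √((0.60 × 0.40 + 0.48 × 0.52) / 229) = 0.0462
- Power = Φ((0.12 − 1/229 − 1.645 × 0.0466) / 0.0462) = 80.06%

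The stated figure reproduces. It belongs to the primary test, which this point leaves alone.

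**2. What an interval would show with no true difference.** Half-width = 1.96 × √(2p(1 − p)/n):

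| Event rate, both arms | 229 per arm | 100 per arm |
|---|---|---|
| 5% | 1.96 × √(0.095/229) = ±4.0 points | 1.96 × √(0.095/100) = ±6.0 points |
| 10% | 1.96 × √(0.18/229) = ±5.5 points | 1.96 × √(0.18/100) = ±8.3 points |

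At 5% observed in both arms, the upper limit against a usual-care rate of 5% is 5 + 4.0 = 9.0% in the larger cohort (1.8 times) and 5 + 6.0 = 11.0% in the smaller (2.2 times).

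**3. What the planned test would do under a true harm.** Take 5% on usual care and 10% on aerosol, and a one-sided test for benefit. With 229 per arm, the null SE is √(2 × 0.075 × 0.925 / 229) = 0.0246 and the alternative SE is √((0.0475 + 0.09)/229) = 0.0245.

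- P(benefit test rejects) = Φ((−0.05 − 1.645 × 0.0246)/0.0245) = 0.01%. With 100 per arm it is 0.14%.
- A two-sided 5% test has power 53% with 229 per arm and 27% with 100 per arm. For 10% v 20% the figures are 85% and 51%.

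The planned test is almost certain to return a non-significant result. A two-sided test would also miss the smaller harm about half the time or more, so the interval matters more than the sidedness.

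**4. One illustration in whole counts.** With 229 per arm, 11 v 23 events gives a one-sided benefit p of 0.98 and a two-sided p of 0.032. With 12 v 23 the values are 0.97 and 0.053. With 100 per arm, 5 v 10 gives 0.91 and 0.18. Two-sided significance turns on a single event in the larger cohort, so no weight is placed on it.

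**5. What a formal equal-safety claim would need.** For a non-inferiority comparison (one-sided 2.5%, 80% power, equal rates), n per arm = (1.96 + 0.842)² × 2p(1 − p)/margin²:

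| Event rate | 5-point margin | 10-point margin |
|---|---|---|
| 5% | 299 | 75 |
| 10% | 566 | 142 |

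The 5-point margin is out of reach in both cohorts at these rates. The 10-point margin is within reach of the larger cohort at both rates, and of the smaller cohort only at the 5% rate. At a 5% event rate, however, a 10-point margin would tolerate a rate of 15%, three times as high.

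**The case against.** A reader might infer that the plan cannot detect harm at all. The documents do not support that. Section 4.6 suspends recruitment at a site after any adverse event that ends aerosol therapy and provides for suspending the whole trial. Section 8.3 requires reporting of severe unexpected events, and under section 9.3 the committee can prompt suspension or discontinuation. Section 9.1 also plans frequencies and relative frequencies for all categorical variables, so an imbalance would be visible if the tables are split by arm. A one-sided p-value near 1 would itself tell an attentive reader that the trend is adverse.

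These safeguards are real, but they do a different job. They centre on events during or from aerosolization. The expedited reporting in section 8.3 covers aerosol-assigned patients only, and section 9.3 excludes termination for events unrelated to giving the aerosol. None of them compares the arms.

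Three further points for the plan:

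- The benefit direction of the secondary tests is inferred from the superiority design and the protection wording. It is not stated.
- Descriptive safety reporting is a common choice, and nothing in the plan says that non-significance will be read as safety. The mismatch arises because objective (c) claims more than description can deliver.
- Section 9.1 says a detailed SAP will be developed, and section 7.1 lists a comparison of pulmonary complications to 7 days. Intervals could still be added. The present text, however, already fixes one-sided testing and limits the adverse event analysis to tabulation.

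**Conclusion.** The point holds in this form: the analysis plan contains no comparative inference on harm and so cannot support objective (c). That follows from the text alone. There is no margin, no between-arm interval and no two-sided comparison for any safety outcome, and death and/or BPD has no analysis at all.

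The size rests on assumed event rates. At 5% in both arms, differences of up to about 4 points (229 per arm) or 6 points (100 per arm) would remain compatible with the data, and more at higher rates. Absence of significance would therefore not establish equal safety in either cohort. No dropout was applied, because the documents state none. The primary efficacy conclusion is not affected.

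**What to change.** In section 9.1:

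- Report every secondary and safety outcome, including death and/or BPD, air leak and pulmonary hemorrhage, by arm within each cohort, with the between-arm difference and a two-sided 95% confidence interval.
- Use two-sided p-values for secondary outcomes where harm is possible.
- Name the analysis for death and/or BPD.

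In section 3, reword objective (c) as estimating the difference in safety outcomes between aerosol and usual care. If the sponsor wants to keep the equal-safety claim, a margin would have to be justified and fixed in advance, and the working above shows how demanding that is at these cohort sizes.

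The cost is SAP wording and a few table columns. Secondary benefit claims lose a little power and the safety claim becomes more modest. The primary test and both sample sizes are unchanged.

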9.2 Sample size justification

In order to gauge the adequacy of the proposed sample size, the statistical power based on the proposed superiority analyses described above was determined. Power in this context is defined as the probability of deeming the experimental treatment superior to active control after performing the test for superiority on the study data at the conclusion of the study, done in conjunction with a 5% nominal significance level. For the sake of simplicity, calculations corresponding to the test based on the proposed approach are approximated by those of a simple two-sample binomial test. We assume the intubation probability corresponding to the active control group to be 60%. This is based on an abstract presented at the Pediatric Academic Societies meeting of 2016 in which the incidence of intubation and instillation of surfactant among infants with early RDS requiring 30 - 40% oxygen was 32 of 50, 64%. A clinical meaningful effect in the uninstalled cohort is defined as a 20% decrease (in percentage points) in the intubation rate which equates to a 48% intubation rate. Calculations show a sample size of 229 per group (458 total) in this cohort will result in a test procedure which is associated with power of approximately 80.1%. In the post-instilled cohort, 200 subjects will be enrolled. This will provide approximately 80% power is detecting a 30% decrease in the intubation rate (60% versus 42%).

9.3 Criteria for trial termination

There will be no termination of the trial for early efficacy. Criteria for termination for futility are presented in 9.1 in interim analysis. The data monitoring and safety committee will review the adverse events and will recommend to the study chair and the sponsor that the trial be suspended or discontinued for safety. Since this is a study of an alternative

method of administration of Infasurf which is FDA approved as safe and effective termination for adverse events unrelated to administration of the aerosol is not included.

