2. BACKGROUND INFORMATION

2.1 Test Drug & Test Device

Infasurf® (calfactant) Intratracheal Suspension for intratracheal use only is an FDA approved drug for the prevention and treatment of the Respiratory Distress Syndrome (RDS). It has no contraindications. It has no identified toxicity. Administration of Infasurf is associated with occasional complications of cyanosis, alterations in heart rate and blood pressure, airway obstruction and reflux of the surfactant. Currently, administration of Infasurf requires endotracheal intubation for intratracheal instillation.

The Solarys® aerosol generator is an FDA approved medical device for delivery of aerosolized drugs to the lungs of intubated patients. The proximal tip of the device has been imbedded in a pacifier shaped adaptation so the Infasurf aerosol can be delivered into the oropharynx and not into the respiratory support air flow at the nares.

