4.6 Stopping Rules

Individuals: Aerosolization will require the usual bedside monitoring by NICU devices and personnel appropriate for all patients in the first hours of life with significant respiratory difficulty. Any patient, who in the judgment of the clinical care team, is experiencing an adverse event due to the aerosolization will have it stopped and not restarted. Taking appropriate remedial steps to resolve an adverse event will be the responsibility of the patient’s clinical care team. The patient will not receive additional aerosol therapy if dosing is discontinued due to an adverse event.

Sites. Following an adverse event resulting in discontinuation of aerosol therapy, recruitment by that site will automatically be suspended.

The Principal Investigator (or a co-investigator) will notify the sponsor within 24 hours of the adverse event. The Sponsor will notify the Study Chair and the Chair of the Data Monitoring and Safety Committee (DMSC) within 24 hours of receiving notification.

The site will not re-start recruiting to the study until the site P.I., the Study Chair and the Sponsor decide that appropriate remediation, if necessary, has been achieved.

Any adverse event during aerosolization will be reviewed by the NICU Medical Director at the site within 24 hours of occurrence. S(he) shall contact and consult with the Study Site P.I. and after that review either allow the study to continue recruiting or suspend the study. In either case the local IRB and the Medical Director of the Sponsor will be notified within 24 hours. If the study is suspended it will not be restarted until the NICU medical director, the site P.I., the local IRB, and the Sponsor have all approved the decision to restart the trial at that site.

In addition, if the study is suspended at any one site the Sponsor will notify the P.I. at all other participating sites and the national and all local IRBs. Any local IRB, site P.I. or the Sponsor can suspend the study at any or all of the other participating sites. If suspended at other sites restarting will require prior approval by the local IRB and P.I. and the Sponsor.

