8. ASSESSMENT OF SAFETY

8.1 Parameters

Adverse Events During Aerosolization.

- 1) Discontinuation of aerosolization before the full dose is given for any reason
- 2) Incidence, magnitude and duration of adverse cardiopulmonary effects:
 - (A) Hypoxemia defined as O₂ saturation of < 80 % for >1 minute despite interventions.
 - (B) Airway obstruction defined as blockage of ventilation for >1 minute producing hypoxemia and bradycardia and requiring endotracheal suctioning and/or re-intubation.
 - (a) during Infasurf aerosolization(s)
 - (b) during instillation(s)
 - (C) Other.

Other safety parameters: These data will be extracted from the medical record of each patient from birth to 28 days of life, death or discharge (whichever is first).

- 1) Incidence of pneumonia, sepsis or other major infection to 28 days
- 2) Incidence and severity of seizures, brain hemorrhages or other brain injuries
- 3) Incidence and severity of necrotizing enterocolitis
- 4) incidence and severity of bronchopulmonary dysplasia.
- 5) Incidence and severity of any other severe unexpected adverse events.

8.2 Methods Identification of all safety outcomes will be by review of the patient’s medical record.

8.3 Analysis Severe, unexpected adverse events. Any severe, unexpected adverse event occurring to aerosolized assigned patients will be immediately reported to the medical director of a participating site. The medical director will review the adverse event and determine if it is related, or possibly related, to the administration of aerosolized Infasurf. If the event is considered “related” or “possibly related” the sponsor will be immediately notified and will be responsible for filing the appropriate notification to FDA. The sponsor will provide the same information to the study chair and to the other study sites. The local site P.I. will be responsible for providing the local IRB with the information about the event.

Non-serious adverse events By regulation an “adverse event means any untoward medical occurrence associated with the use of a drug in humans, whether or not considered drug related.” (21 CFR 312.32(a)).

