Interim analysis. A group sequential approach will be utilized in the statistical evaluation of data, with a two interim analyses and the final analysis planned. The interim analyses, which will assist in making the decision of whether or not to stop the trial early for futility, will take place after the study outcome variables are observed in approximately the first 1/3 of evaluable subjects and after approximately 2/3 of evaluable subjects. Assuming increasing recruitment during the months and allowing for data clean up and statistical analysis, we anticipate the interim analysis will be performed at approximately 4 months after enrollment of the first patient. The principal interim analyses will involve the computation of the conditional power pertaining to the test of the primary efficacy outcome, that is, we will compute the probability of rejecting the primary null hypothesis at the end of study given the data observed thus far. In the event of unfavorable trends in the data, the conditional power of achieving a final conclusion of superiority will be much less than the initial planned power of the study for a given point in the alternative parameter space, thus making conditional power a quantitative tool for use in interim decision making. Monte Carlo simulations based on 10,000 iterations will be utilized to compute the conditional power under two difference scenarios: 1) assuming the parameter values utilized for sample size derivation, and 2) assuming the true parameter values are equal to the sample estimates computed from the interim data. Given the uncertainty in the actual values of the parameters, the conditional power associated with the second scenario should be viewed as that which is most informative in decision making. Additionally, 95% confidence intervals will be obtained and used to assess if the values assumed in the planning of the study are much different than those suggested by the data. The conditional power for selected values within the computed confidence intervals may be calculated if deemed potentially informative. Results of interim analyses will be reviewed by the Data and Safety Monitoring Board. After the second interim analysis, sample size may be modified using the method discussed in Gould (1992),⁷ performed in conjunction with an effect size of a 20% decrease in intubation rate.

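### Section 9.3 rules out stopping for events unrelated to the aerosol without saying that an aerosol-arm excess counts, and no by-arm safety table is scheduled before study end

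*Combined protocol and SAP*

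**What the plan says.** Section 9.3 gives the committee a general safety role. It reviews adverse events and "will recommend to the study chair and the sponsor that the trial be suspended or discontinued for safety". The next sentence narrows this: because Infasurf is already approved and only its delivery is new, "termination for adverse events unrelated to administration of the aerosol is not included". The word unrelated is not defined.

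Section 2.1 describes the approvals. For the drug: "Intratracheal Suspension for intratracheal use only is an FDA approved drug". The nebulizer is an "approved medical device for delivery of aerosolized drugs to the lungs of intubated patients", and it has been modified for this trial.

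Other provisions that bear on safety review:

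- **9.1, Primary safety analyses:** "All adverse events will be recorded during the study period and then tabulated at the end of the study".
- **9.1, Interim analysis:** two looks, at about 1/3 and 2/3 of evaluable subjects, to inform a futility decision. "The principal interim analyses will involve the computation of the conditional power pertaining to the test of the primary efficacy outcome". The results go to the Data and Safety Monitoring Board.
- **8.3:** "Any severe, unexpected adverse event occurring to aerosolized assigned patients will be immediately reported to the medical director", who then decides whether that event is related or possibly related.
- **4.6:** "Following an adverse event resulting in discontinuation of aerosol therapy, recruitment by that site will automatically be suspended". The trial-level conference has the same trigger.
- **Section 3, objective (c):** aerosolized Infasurf is to be shown as safe as usual care.

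**The concern.** Objective (c) is a comparison between arms. Brain hemorrhage, necrotizing enterocolitis, air leak and infection can occur in either arm, so a single case can rarely be attributed to the aerosol with confidence. A moderate excess shows mainly when the arms are set side by side. If the 9.3 exclusion is applied one case at a time, each event can be called unrelated and the excess is never weighed.

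The stated reason does not carry the exclusion. Both approvals, as 2.1 describes them, are for conditions that differ from the trial's: aerosol into the oropharynx of non-intubated infants, through a modified device. A harm of the strategy as a whole, for example from later instillation of surfactant, would be an effect of allocation that need not look related to any one aerosol session.

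At stake is whether the committee sees such an excess, and regards it as a ground for acting, while infants are still being enrolled.

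**Working it through.** **1. The text.** I set each safety provision against two questions: does it compare arms, and does it operate before the end of the study?

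| Provision | Compares arms? | Before study end? |
|---|---|---|
| 9.3 committee review | Not stated | Yes, timing and content not set |
| 9.1 safety tabulation | Not stated | No |
| 9.1 interim looks | Yes, primary outcome only | Yes |
| 8.3 urgent reporting | No, aerosol infants only | Yes |
| 4.6 suspension triggers | No, need an aerosol event | Yes |

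No provision is specified to do both for safety events, and none says that an arm excess bears on relatedness.

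**2. Size of the looks.** The plan's 229 per group reproduces at 60% v 48%, one-sided 5%, 80% power: 213 without and 229 with continuity correction. This point does not dispute it. Both cohorts: 458 + 200 = 658, or 329 per arm.

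- Pooled: about 110 and 219 per arm at 1/3 and 2/3.
- Uninstilled cohort (229 per arm): 76 and 153.
- Post-instilled cohort (100 per arm): 33 and 67.
- Infants not yet enrolled: at most 658 - 219 = 439 and 658 - 439 = 219. Recruitment during data cleaning lowers both. At a flat 80 a month for the 4 months named in 9.1, 658 - 320 = 338 at the first look.

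**3. What by-arm tables could show.** The documents give no safety event rates, so all rates here are assumed. Two-sided p<0.05 is a yardstick, not a proposed rule. Pooled-variance z test:

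power = Φ{ [d - 1.96·√(2p̄(1-p̄)/n)] / √[(p₁(1-p₁) + p₂(1-p₂))/n] }

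For 5% v 10% at n = 110: d = 0.05 and p̄ = 0.075; the null SE is √(0.13875/110) = 0.0355 and the alternative SE is √(0.1375/110) = 0.0354. Then (0.05 - 0.0696)/0.0354 = -0.555 and Φ = 0.29.

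Events are sparse (5.5 v 11 expected in that example), so I also summed the product of the two binomial probabilities over every pair of counts for which Fisher's exact test gives p<0.05.

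| Chance of p<0.05, Fisher to pooled z | First look | Second look |
|---|---|---|
| Pooled, 5% v 10% | 21-29% | 45-51% |
| Pooled, 5% v 15% | 64-70% | 93-94% |
| Uninstilled, 5% v 10% | 13-21% | 31-38% |
| Post-instilled, 5% v 10% | 2.5-12% | 11-19% |

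**4. Incomplete follow-up.** Suppose data are cut when the last infant reaches 72 hours. Infants short of 28 days (unless discharged) number monthly accrual × 25/30.4. At 658/12 = 54.8 to 80 a month that is 45 to 66, leaving (219 - 66)/2 = 77 to (219 - 45)/2 = 87 per arm at the first look and 187 to 197 at the second. Pooled-z power for 5% v 10% becomes 22-24% and 45-47%. Only 54.8 × 5/30.4 = 9 to 80 × 5/30.4 = 13 infants would lack day 8.

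**5. Chance imbalances.** I simulated 200,000 trials with five independent event types at 5% in both arms and looks at 110 and 219 per arm. |z|>1.96 occurred at least once in about 33% of trials, and in the direction against aerosol in about 18%.

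**The case against.** The strongest reply is that 9.3 already supplies the safeguard. The committee's review is not limited by arm, event type or method of attribution. In a randomized trial a credible excess in the aerosol arm is itself evidence of relatedness, so the exclusion need not reach it. The case-by-case step in 8.3 belongs to the site medical director, serves FDA notification and includes possibly related events; it is not stated as the committee's standard. This stands, and it is why the point concerns an ambiguous rule rather than an absent safeguard.

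Second, the detail may sit elsewhere. Section 9.1 promises a further SAP, and a committee charter, if there is one, is not among the documents. The trial is unmasked, the case report form records the arm, and outcomes are extracted for every infant. Section 9.1 calls conditional power the principal interim computation, not the only one, and times the looks after outcome variables in the plural, so 28-day data might be complete. All fair, but none of it schedules the comparison or settles what 9.3 means.

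Third, the plan relies on more than approval: unchanged composition and activity (2.3, 4.4), a lower lung dose than instillation (6.1), and over 30 pilot infants with no interference with breathing requiring discontinuation (2.3). That is relevant to product and procedural risk. It does not address a between-arm excess of 28-day events.

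Fourth, the detection figures rest on assumed rates, depend on the test, and pool cohorts that 9.1 treats almost as separate trials. This also stands. They give scale only.

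A reader might infer that the committee is barred from stopping on an imbalance, may not see by-arm data, or reviews no safety data until the end. The documents support none of these: 9.3 provides for review during the trial, and nothing prohibits by-arm tables.

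**Conclusion.** The point holds as a gap in a stated rule. Section 9.3 excludes a class of events without defining it and justifies this by approvals given for other conditions of use. The rest of the plan provides only case-level attribution in one arm, plus a tabulation after enrolment is over. An aerosol-arm excess of serious events could be set aside without departing from the text, although a sensible committee could read the text otherwise.

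The conclusion rests on the wording and needs no event rate. As for scale, scheduled tables would probably reveal a large excess (5% v 15%, pooled) by the second look, would detect a doubling from 5% in roughly a quarter of trials at the first look and half at the second, and would usually miss a doubling within one cohort. These are illustrations under assumed rates and, in the main table, complete follow-up. Modest power argues against a formal threshold, not against showing the comparison. The sponsor should make the change; it does not affect the efficacy sample size or significance level.

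**What to change.** 1. Reword 9.3 so that a between-arm excess of deaths or severe adverse events is a ground for a safety recommendation, whatever the attribution of individual cases.
2. At the existing 1/3 and 2/3 looks, give the committee by-arm tables, for each cohort and pooled, of deaths, severe events among the 8.1 parameters and the 7.2 pulmonary complications, collected the same way in both arms.
3. Use the day 4, day 8 and day 29/discharge columns already in section 7 of the case report form, and show how many infants per arm have been followed to each.
4. Set no p-value trigger; leave the recommendation to the committee's judgment.

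Cost: one sentence and one set of tables at two looks already planned, from data already extracted for every infant. The downsides are earlier data work for usual-care infants, incomplete 28-day data for recent enrolees, and chance imbalances (about one trial in three under the assumptions above), which the committee should be told to expect. The tables will still often miss small excesses, especially within one cohort.
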